## **Secondary Aims:**

**To examine the perceived effectiveness of all the warning labels.** A personalized effectiveness ranking for each participant will be collected by asking them to rank their top 3 warning labels on being most avoidant, preferred and informative.

## **4 Study Design**

### ***4.1 Design***

Study participants will be randomized to view one set of graphic warning labels with either lesser-known or well-known harms of tobacco use. The labels will be presented on a computer screen while their eye movements are recorded for each label seen. Participants will provide smoking and quitting related attitude, belief and intention measures and answer questionnaires before and after viewing the labels during the in-person session. This laboratory-based study will aim to enroll 70 current cigarette users to complete a 1-day, randomized, parallel design protocol. We base this design on our previous and ongoing studies using eye-tracking methodology.

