## 1 Study Summary

Title	PILOT: Evaluation of the new FDA warning labels: Does highlighting lesser known harms of tobacco use increase attention, recall and knowledge of tobacco harms compared to well-known harms?
Short Title	FDA Labels: Eye Tracking Study
IRB Number	843703
Methodology	
This laboratory-based study will aim to enroll 70 current cigarette users to complete a 1-day cross-sectional, randomized, parallel design protocol.
 
The participants will be randomized to one of two conditions, pictorial warning labels (PWLS) with well-known versus lesser-known tobacco harms. After completing a baseline questionnaire, the participants will view about 4 labels from the assigned group and complete a follow-up questionnaire. Eye-tracking equipment will provide data on visual processing of the warning labels and the effect of these labels on knowledge, attitudes and beliefs about smoking will be supplemented by self-report.

Study Center(s)	Single-center
Objectives	
Aim 1: To assess daily smokers' response to FDA PWL content on visual engagement, recall and knowledge
 
Aim 2: To conduct a laboratory-based study to evaluate effects of PWL risk content (lesser-known vs well-known risks) on visual engagement, recall and knowledge

Number of Participants	70 participants (randomized)

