## 2 Introduction

### 2.1 Background

The Food and Drug Administration (FDA), while implementing a provision of the Family Smoking Prevention and Tobacco Control Act (TCA), issued new cigarette health warnings for cigarette packages on August 15, 2019 (84 FR 42754). Pictorial warning labels (PWLs) are an effective way to communicate health risks of tobacco use  and research evidence from many countries shows a significant increase in awareness of smoking harms as a result of PWL exposure . Multiple research studies have emphasized the effectiveness of pictorial warning labels compared to text-only warnings for increasing knowledge regarding smoking risks, likelihood to reduce cigarette demand and promoting quitting . Despite the general assumption that smokers are aware of risks associated with smoking, even in high income countries such as United States and Canada – significant gaps in health knowledge remain . The newly released warning labels include lesser-known harms of smoking such as macular degeneration, bladder cancer and erectile dysfunction. Currently, there is limited evidence on the effect of lesser-known harm warnings on attention, recall and knowledge increase of tobacco related harms.

This study, as a part of Pilot Project of the Tobacco Centers of Regulatory Science (TCORS), will examine the effect of the newly proposed FDA PWLs on daily smokers on visual engagement, knowledge, and recall.

It is as an exploratory experimental study using objective measures and self-report survey. We will recruit 70 daily smokers to participate in a single-session laboratory-based study. The participants will be assigned to either the lesser-known harm group or well-known harm group of PWLs. They will first view 4 warning labels in a randomized order from the assigned group following which they will view all 11 warnings and rank them based on avoidance, preference and being most informative. Primary outcomes will be eye-tracking measures, correct recall of text, image and message, knowledge of tobacco harms and risk-perceptions.

**This document is a human research protocol for a TCORS Pilot Study.** This study will be conducted in compliance with this research protocol and according to U.S. standards of Good Clinical Practice (GCP), applicable government regulations, and institutional research policies and procedures.

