## **2.2 *Rationale***

### **2.2.1) Rationale for between subject condition – warning labels**

The new warning labels are created in compliance with court recommendations and tailored to increase knowledge of smoking harms. 6 out of 11 warning labels highlight lesser-known smoking harms. The participants will be randomized to one of two conditions – one containing FDA warning labels bearing lesser known and another with better-known tobacco use risks. In Canada, packages include information about smoking causing impotence and therefore, twice as many respondents reported impotence as tobacco harm relative to respondents in US, UK and Australia. There have been no previous studies that have evaluated the impact of highlighting lesser known harms of tobacco; they are now a part of FDA's label policy and would add to the literature on tobacco control messaging.

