### **2.2.2) Rationale for primary outcome measures**

Previous PWL studies using eye-tracking methodology have used latency, latency duration and total dwell time to characterize visual engagement and this study will continue to use these measures for consistency and comparisons. The image/text/message recall and knowledge measures are a good indicator of information retention and effectiveness of the labels.

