## **3 Study Objectives**

**Aim 1:** To assess daily smokers' response to FDA PWL content on visual engagement, recall and knowledge.

H1a: Warning label images may have greater visual engagement when compared to text portions of the PWLs

H2a: The recall for image areas of PWLs might be higher post-exposure in comparison to text areas of interest.

**Aim 2: To evaluate effects of PWL risk content (lesser-known vs well-known risks) on visual engagement, recall and knowledge**

H2a: Warning labels bearing images of lesser known tobacco use harms will have longer latency and fixation durations than warning labels bearing images of well-known harms of tobacco.

H2b: The initial image/text/gist recall of PWL text and message with lesser known harms may be lower than well-known harms.

H2c: The knowledge increase will be greater among smokers exposed to warning labels highlighting lesser known harms of tobacco.

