### **5.10 Analytic Plan**

Descriptive statistics will be used to characterize the study population and smoking-related data. A factorial design will be used. The primary independent variable is warning label type (lesser-known harms vs well-known harms. Associations of independent and covariate variables with eye-tracking measures, recall, and knowledge will be assessed using unpaired t-tests or ANOVA (categorical predictors) and linear regression analysis (continuous predictors). Eye-tracking measures are continuous, and previously been observed to meet assumptions of normality. Recall is dichotomous and will be examined using logistic regression model to generate odds ratio, as in our previous work (Strasser et al., 2012; 2008). A primary outcome measure of this study is change in knowledge after exposure to graphic cigarette warning labels. This measure will be continuous when calculated on a scale and categorical when coded as increase in knowledge vs no change. Chi-square and regression analysis can be used to assess association of knowledge change with label type and by age group. Analysis will be conducted in a using Stata (Stata Corp., TX). Path analysis techniques for tobacco related mediation and moderation models will be used; covariates found to be significantly associated will be considered for inclusion in models as appropriate.

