## **6 Risk / Benefit Assessment**

Although cigarette smoking is associated with many diseases, we do not anticipate that any risk of smoking 1 cigarette during a study session is beyond the everyday risk to all participants who need to be smoking at least 5 cigarettes daily to be eligible for the study. The anticipated benefit of this study, in general, is to evaluate the effectiveness of graphic warning labels. Results from this study may then be used to guide FDA regulation of the images used on cigarette packs. Others will be able to potentially benefit from this study by having improved tobacco policy put into effect that will reduce the impact of cigarette smoking on the US population.

The potential benefits of this study outweigh the potential risks. There is only a minimal risk of experiencing study-related AEs or SAEs by enrolling in this trial. In addition, we will minimize any risks related to loss of privacy by maintaining strict confidentiality. Results from this trial, however, may have scientific and policy implications by providing empirical support for FDA policy on cigarette packaging regulation in tobacco products and educating smokers on the risks of smoking.

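### Do the unlisted label sets, the unstated selection rule and the missing recognition score undermine the Aim 2 comparison?

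*Combined protocol and SAP*

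**What the plan says.** Section 4.1 (Design) defines the intervention: "Study participants will be randomized to view one set of graphic warning labels with either lesser-known or well-known harms of tobacco use". Section 2.1 (Background) gives the number and randomizes the order: "They will first view 4 warning labels in a randomized order from the assigned group". Section 1 (Study Summary) is looser: "the participants will view about 4 labels from the assigned group". Section 2.2.1 gives the pool: "6 out of 11 warning labels highlight lesser-known smoking harms", which leaves 5 well-known labels by subtraction. Section 2.1 names three lesser-known harms, as examples only.

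Aim 2 in Section 3 concerns risk content. H2a, for instance, reads "Warning labels bearing images of lesser known tobacco use harms will have longer latency and fixation durations". Section 5.10 adds "The primary independent variable is warning label type" and has no term for the individual label. Section 6 looks ahead: "Results from this study may then be used to guide FDA regulation of the images used on cigarette packs".

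On memory outcomes, Section 2.2.2 says "The image/text/message recall and knowledge measures are a good indicator of information retention and effectiveness of the labels". Section 5.9.2 describes an open-ended recall question and, in the same paragraph, a task of picking out the labels and statements seen from all 11. Section 5.10 treats recall as dichotomous and does not mention recognition.

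**The concern.** The label set is the intervention. With 4 labels per arm, many sets fit the text, and a reader cannot tell which pictures and statements would have produced an arm difference, nor repeat the exposure. If everyone in an arm sees the same 4, harm type cannot be separated from the particular labels chosen. A t-test between participants ignores label-to-label variation, so a finding on 8 labels could be reported as a finding on lesser-known harms as a class, with a p-value that is too small for that claim.

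The recognition task looks like a second gap. It stands under the primary-outcome heading without a scoring rule, and the arms differ in how many labels of their own type go unseen.

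**Working it through.** **1. Inputs.** From the documents: 11 labels, 6 lesser-known (Section 2.2.1), 4 shown (Section 2.1) or about 4 (Section 1), 70 randomized (Section 1). Assumed: 35 per arm (no ratio is stated), two-sided 5%, and one label-averaged eye-tracking value per participant. Outcome variance is split into a participant share s_p = 0.40, a label share s_L of 2%, 5% or 10%, and the remainder s_e = 0.60 − s_L. The documents give no variance figures, so these shares are illustrative.

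**2. Counting.** With fixed sets of 4, C(6,4) × C(5,4) = 15 × 5 = 75 pairs of sets fit the text. Labels shown: 4 + 4 = 8 of 11. Not shown: 2 lesser-known and 1 well-known. If 4 are drawn for each participant instead, all 11 are covered, with about 35 × 4/6 = 23 viewers per lesser-known label and 35 × 4/5 = 28 per well-known label. No passage says the set is fixed, so 8 of 11 is conditional.

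**3. Type I error by reach of the conclusion, fixed sets of 4.** The variance that the test allows for is T = 2 × (s_p + s_e/4)/35. The label variance left out is O:

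- labels shown: O = 0
- the FDA's 11: O = (s_L/4) × [(1 − 4/6) + (1 − 4/5)] = (s_L/4) × 0.533

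The error is 2 × [1 − Φ(1.96/√(1 + O/T))].

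| s_L | T | O for the 11 | O/T | Error, labels shown | Error, the 11 |
|---|---|---|---|---|---|
| 2% | 0.03114 | 0.00267 | 0.086 | 5% | 6.0% |
| 5% | 0.03071 | 0.00667 | 0.217 | 5% | 7.6% |
| 10% | 0.03000 | 0.01333 | 0.444 | 5% | 10.3% |

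A simulation of 20,000 runs gave 4.8%, 5.0% and 4.8% for the labels shown, and 5.9%, 7.6% and 9.9% for the 11.

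**4. Sensitivity.** With participant shares from 30% to 60%, the 11-label error runs from 5.8% to 11.2%. With label shares of 0.5% and 1% it is 5.2% and 5.5%. With 5 labels per arm, only one lesser-known label is unseen: O = (s_L/5) × (1 − 5/6) and T = 2 × (s_p + s_e/5)/35. At s_L = 2% this gives O/T = 0.00067/0.02949 = 0.023 and 5.3%. At 10% it gives 0.00333/0.02857 = 0.117 and 6.4%.

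**5. Which outcomes this covers.** The model fits a continuous measure averaged over labels, such as eye tracking. Recall is dichotomous, and knowledge is one checklist per person before and after exposure. The percentages do not carry over to either.

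**6. Recognition.** The scoring rule would matter if recognition were the tested outcome. Answering that every label was seen scores 4/11 = 36% correct over 11 labels, but 100% on hits alone. A participant who guesses purely by label type makes false alarms on 2/7 = 29% of unseen labels in the lesser-known arm and 1/7 = 14% in the other.

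The plan does not point to recognition as the H2b outcome. H2b in Section 3 is about initial recall of image, text and gist, and picking labels from a list does not measure gist. Section 5.8 puts the recall task directly after exposure (step 6) and recognition, together with ranking, in the following step (step 7). Sections 2.1 and 2.2.2 also speak of recall.

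**The case for a change.** The strongest case for a change is that an unlisted intervention is a real defect even in a pilot, and that Aim 2 and Section 6 invite a reading broader than 8 labels. If the claim were about lesser-known harms beyond the FDA's labels, the omitted variance would be O = 2 × s_L/4. At s_L = 10% that is 0.05, O/T = 1.667, and the error is 23.0%. At 2% and 5% it is 8.8% and 14.6%.

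That arithmetic is sound, but it answers a wider question than the plan asks. The study title, Section 2.1, Section 2.2.1 and Aim 1 all concern the FDA's labels, and Section 6 says only that results may inform regulation of images on packs.

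The design alternatives do not clearly improve matters. Treating label as a random effect with only 8 labels would raise the difference detectable with 80% power from 0.68 to about 0.80, 0.96 or 1.20 SD for the three label shares. Drawing 4 labels per participant restores about 5% for the 11, but it needs areas of interest and recall coding for 11 labels instead of 8, and it varies the harms each person sees before the knowledge test (H2c). By-label summaries use data already collected and are descriptive only: for an assumed recall of 60% among 35 viewers, the 95% interval is ±1.96 × √(0.6 × 0.4/35) = ±16 points.

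What stands is that the label list, the exact number, the selection rule and a recognition score are absent from the available text. The report will need to supply them.

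**Conclusion.** No change to the plan follows. A fixed set per arm is a legitimate design, and the randomized comparison of the labels shown is valid at 5%. For the FDA's 11 labels the excess error is modest: 6.0% to 10.3% with 4 per arm and 5.3% to 6.4% with 5, under the assumed label shares of 2% to 10%, a participant share of 40% and 35 per arm. It applies only to label-averaged eye-tracking measures, and only if the sets are fixed, which the text suggests but does not state.

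The missing details are ones that analysts fill sensibly. The sets must exist before the first session and can be listed in the report, the conclusion can be worded for the labels shown, and H2b already rests on open-ended recall, with recognition reported separately. None of this alters the design, sample size, tests or results of a pilot that describes itself as exploratory.

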### ***4.2 Study Duration***

Recruitment/enrollment is anticipated to begin in November 2020. We estimate that up to 70 participants will be randomized and complete the study within a year. Each participant will attend the single, 2-hour study session.

## **5 Characteristics of the Study Population**

### ***5.1 Target Population***

Participants will include 70 daily smokers aged 21-65 who report currently smoking cigarettes and have been smoking at least 5 cigarettes daily for at least the last year.

### ***5.2 Accrual***

We have ongoing projects with current smokers who meet the criteria for the study. At the conclusion of those studies, we ask participants if we can contact them regarding future research opportunities. Further, we will post flyers and advertise online, similar to our previous recruiting efforts. We will enroll (i.e., sign an IRB-approved informed consent form) ~70 participants to . To achieve this goal, we intend to recruit 5-7 participants per month, which will allow us to enroll and randomize enough participants to complete data collection as proposed. The sample size was determined based on a previous graphic warning label eye-tracking study by Mercincavage et al.

and Lochbuehler et al. which was sufficiently powered to detect effects of a content attribute (congruency) on eye-tracking measures and image/text/message recall. In order to maximize participation in the study we will: (1) educate participants about the benefits of participation and the knowledge gained from the study; (2) schedule sessions at times convenient for participants; (3) provide reminder calls, emails, and potentially texts; and (4) provide payment for completion of the study visit and study requirements.

### **5.3 Key Inclusion Criteria**

1. Current cigarette smokers using only filtered commercially manufactured cigarettes; smoking at least 5 cigarettes daily and smoking for at least last 1 year.
2. Age greater than 21 years and less than or equal to 65 years.
3. Participants must physically present a pack of their preferred brand of cigarettes at the lab session to confirm their status as a cigarette smoker.
4. Not currently undergoing smoking cessation treatment or planning to quit smoking currently or in the next month.
5. Plan to live in the area for the duration of the study.
6. Capable of giving written informed consent, which includes compliance with the requirements and restrictions listed in the combined Informed Consent and HIPAA form.
7. Able to communicate fluently in English (i.e., speaking, writing, and reading) as determined by the research assistant.
8. Male, female, non-binary or other.

### **5.4 Key Exclusion Criteria**

Participants who do not meet the inclusion criteria or present and/or self-report with the following criteria will not be eligible to participate in the study. After final eligibility is confirmed, participants who present and/or self-report with any of the following exclusions during the study period may only remain eligible after the case is reviewed by Principal Investigator and it is determined that the situation does not significantly impact the study design, data quality, and/or participant safety and welfare.

- Use of any nicotine-containing products other than cigarettes. Participants reporting isolated use of other nicotine containing products less than 5 times per month are eligible to participate.
- Not actively trying to quit smoking currently and had not made a quit attempt in the past month.
- Self-report current alcohol consumption that exceeds 25 standard drinks/week.
- Self-report current pregnancy or breast feeding.
- Any self-reported impairment - visual (colorblindness or impairments such as glass eye), physical, and/or neurological impairments preventing the proper completion of the study procedures.
- Serious or unstable medical condition.
- Lifetime history of schizophrenia, psychosis, and/or bipolar disorder.
- Current use or discontinuation of anti-psychotic medications within the last 6 months.
- Current diagnosis of active major depression. Participants who maintain a diagnosis of major depression who have not experienced any major depressive episodes in the past 6 months and are stable on antidepressant medication(s) are eligible to participate.

- Inability to provide informed consent or complete any of the study tasks as determined by the principal investigator.

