Main Inclusion and Exclusion Criteria	
Main Inclusion:
 

1. Current cigarette smokers who smoke at least 5 cigarettes per day who are between 21 and 65 years of age. Participants must physically present a pack of their preferred brand of cigarettes during the session to confirm their status as a regular cigarette smoker.

2. Not currently undergoing smoking cessation treatment or planning to quit smoking.

 
Main Exclusion:
 

1. Use of any nicotine-containing products other than cigarettes. Participants reporting isolated use of other nicotine containing products less than 5 times per month are eligible to participate.

2. Current or impending enrollment in a smoking cessation program. Further, participants will be excluded for an attempt to quit smoking over the duration of the study period.

3. Lifetime history or current diagnosis of COPD, cardiovascular disease, or heart attack.

 
The complete list of study inclusion and exclusion criteria is included within the Characteristics of the Study Population section of this protocol.

--	--

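### The eligibility lists do not agree: one Section 5.4 exclusion on quitting is worded as an entry condition, and Section 5 omits the summary's COPD, cardiovascular disease and heart attack exclusion

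*Combined protocol and SAP*

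**What the plan says.** **Quit status.** The lead-in to Section 5.4 states that people who "present and/or self-report with the following criteria will not be eligible to participate in the study". The second bullet beneath it reads "Not actively trying to quit smoking currently and had not made a quit attempt in the past month".

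Three other statements address quitting:
- Section 5.3, inclusion 4: "Not currently undergoing smoking cessation treatment or planning to quit smoking currently or in the next month".
- Section 1 (Study Summary), main inclusion 2: "Not currently undergoing smoking cessation treatment or planning to quit smoking".
- Section 1, main exclusion 2, which bars people in or about to enter a cessation program and adds that "participants will be excluded for an attempt to quit smoking over the duration of the study period".

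**Medical history.** Section 1, main exclusion 3, is "Lifetime history or current diagnosis of COPD, cardiovascular disease, or heart attack". The summary then says: "The complete list of study inclusion and exclusion criteria is included within the Characteristics of the Study Population section of this protocol". The nearest item in Section 5.4 is "Serious or unstable medical condition".

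**The concern.** The quit-status bullet is written as something a participant should satisfy but sits in a list of things that disqualify. Applied as printed, it removes the smokers whom the rest of the protocol sets out to recruit. The medical-history exclusion has a different fault: it appears in the summary but not in the section that the summary calls complete.

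These lists are used to make decisions. Section 5.7 has initial eligibility judged against them. Section 5.6 has candidates checked against a registration database for any earlier report that would disqualify them, and recruitment draws partly on past participants. Whether a recorded heart attack removes a candidate at that step depends on whether staff follow Section 1 or Section 5.4. Section 5.8 has each participant smoke a cigarette during the session, so the status of a cardiopulmonary exclusion should not be in doubt. Section 5.4 also calls for review by the principal investigator when a participant meets any listed exclusion after eligibility is confirmed. Under the literal bullet, ordinary participants would trigger that review.

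**Working it through.** There is no figure in the plan to reproduce. The check is a count of items and a logical comparison.

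**1. Count of items.** Section 5.3 has 8 numbered inclusion items. Section 5.4 has 10 bullets: other nicotine products, quit status, alcohol, pregnancy or breast feeding, impairment, serious or unstable condition, lifetime psychotic or bipolar disorder, antipsychotic medication, active major depression, and inability to consent or complete tasks. The total is 8 + 10 = 18. Nine of the 10 bullets describe a reason to exclude, some with a stated exception. One, quit status, describes a condition for entry.

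**2. Logic of the quit-status criteria.** Let P = in cessation treatment or planning to quit, T = actively trying to quit now, and A = a quit attempt in the past month. Section 5.3 requires not-P. Among people with not-P:

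| T | A | 5.4 bullet applied literally | 5.4 bullet taken as an entry condition |
|---|---|---|---|
| no | no | excluded | eligible |
| no | yes | eligible | excluded |
| yes | no | eligible | excluded |
| yes | yes | eligible | excluded |

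The two eligible sets are (T or A) and (not-T and not-A). They do not overlap: everyone eligible under one reading is ineligible under the other. If trying to quit implies planning to quit, the two rows with T = yes drop out. The literal reading then leaves only smokers who made an attempt in the past month but are no longer trying or planning to quit. That group is narrow but not empty, so the lists are not logically impossible to satisfy together.

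**3. Summary exclusions traced into Section 5.**

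| Summary main exclusion | Section 5 |
|---|---|
| 1. Other nicotine products | Repeated word for word in 5.4 |
| 2. Cessation program; quit attempt during the study | Treatment part is addressed by 5.3 inclusion 4; the 5.4 bullet on the same topic runs in the opposite direction |
| 3. COPD, cardiovascular disease, heart attack | Named in 0 of 18 items |

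**4. Does the general medical bullet fill the gap?** "Serious or unstable medical condition" names none of the three diagnoses and has no look-back. The bullet directly after it, on psychotic and bipolar disorders, states a lifetime look-back expressly. Section 5.4 therefore says so when it wants history to count. A past heart attack in someone now well is excluded by Section 1 and not clearly excluded by Section 5.4.

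**5. Could missing text explain it?** Sections 5.3 and 5.4 read as intact, with no sign of redaction, and the removed pages lie outside Section 5.

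**The case against.** The strongest reply is that both points are editorial. Three statements fix the intended direction on quitting, and staff are unlikely to apply a bullet that would bar most of the target population. The medical-history item is an omission rather than a clash: nothing in Section 5 says such people are eligible, and both lists can be applied together. Current disease can be stable and still serious, so the general bullet may catch some of it. The same eligibility rules apply to both randomized arms, so the comparison of label types is not biased. The screener items are not in the documents, so no operational error is shown.

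Much of this is fair, and it limits the size of the point. A misplaced sentence is the likely cause of the first discrepancy. For the second, the gap is clearest for past events; whether stable current disease is covered is arguable. The summary's quit-attempt exclusion and the Section 5.4 bullet also use different time windows: one covers the study period, which is a single 2-hour session, and the other covers the present and the past month. They share a topic and run in opposite directions, but they are not the same criterion reversed.

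The reply does not remove either discrepancy. The past-month look-back appears nowhere else in the eligibility text, so staff who ignore the misplaced bullet lose that condition. And because the summary calls Section 5 complete, two careful readers could screen the same person differently on medical history.

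**Conclusion.** The concern holds, and the text should be corrected. One of the 10 bullets in Section 5.4 is worded in the wrong direction for an exclusion list, and its literal and apparently intended readings select groups with no one in common. One of the summary's three main exclusions is named in none of the 18 items in Sections 5.3 and 5.4.

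The consequence is confined to who is enrolled, how consistently they are screened, and to whom the results apply. No sample size or analysis figure depends on it, and the documents give no basis for estimating how many people are affected. The conclusion rests on the wording of Sections 1, 5.3 and 5.4 alone. Whether the REDCap and telephone screeners carry either error is unknown; they may already be correct.

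**What to change.** 1. Move the quit-status sentence to Section 5.3, or reword it in Section 5.4 so that its direction agrees with inclusion 4 and the summary. The sponsor should confirm that the past-month look-back is intended, since no other eligibility statement contains it.
2. Reconcile main exclusion 3 in Section 1 with Sections 5.3 and 5.4, so that the same rule on COPD, cardiovascular disease and heart attack appears in both places. Which rule applies is for the sponsor to decide.
3. Check the REDCap screener, the telephone screen and the registration-database check against the corrected list.

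The cost is a short protocol amendment and a review of the screener items. No participants or procedures are added.
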